#### 9.2.2 Serious adverse events (SAEs)

A serious adverse event is any untoward medical occurrence or effect that

- results in death;
- is life threatening (at the time of the event);
- requires hospitalisation or prolongation of existing inpatients' hospitalisation;
- results in persistent or significant disability or incapacity;
- is a congenital anomaly or birth defect; or
- any other important medical event that did not result in any of the outcomes listed above due to medical or surgical intervention but could have been based upon appropriate judgement by the investigator. An elective hospital admission will not be considered as a serious adverse event.

The investigator will report all SAEs to the sponsor without undue delay after obtaining knowledge of the events.

The sponsor will report the SAEs through the web portal ToetsingOnline to the accredited METC that approved the protocol, within 7 days of first knowledge for SAEs that result in death or are life threatening followed by a period of maximum of 8 days to complete the initial preliminary report. All other SAEs will be reported within a period of maximum 15 days after the sponsor has first knowledge of the serious adverse events.

### 9.2.3 Suspected unexpected serious adverse reactions (SUSARs)

Adverse reactions are all untoward and unintended responses to an investigational product related to any dose administered.

Unexpected adverse reactions are SUSARs if the following three conditions are met:

1. the event must be serious (see chapter 9.2.2);
2. there must be a certain degree of probability that the event is a harmful and an undesirable reaction to the medicinal product under investigation, regardless of the administered dose;
3. the adverse reaction must be unexpected, that is to say, the nature and severity of the adverse reaction are not in agreement with the product information as recorded in:
  - a. Summary of Product Characteristics (SPC) for an authorised medicinal product;
  - b. Investigator's Brochure for an unauthorised medicinal product.

The sponsor will report expedited the following SUSARs through the web portal ToetsingOnline to the METC:

- SUSARs that have arisen in the clinical trial that was assessed by the METC;
- SUSARs that have arisen in other clinical trials of the same sponsor and with the same medicinal product, and that could have consequences for the safety of the subjects involved in the clinical trial that was assessed by the METC.
- The remaining SUSARs are recorded in an overview list (line-listing) that will be submitted once every half year to the METC. This line-listing provides an overview of all SUSARs from the study medicine, accompanied by a brief report highlighting the main points of concern. The expedited reporting of SUSARs through the web portal Eudravigilance or ToetsingOnline is sufficient as notification to the competent authority.

The sponsor will report expedited all SUSARs to the competent authorities in other Member States, according to the requirements of the Member States.

The expedited reporting will occur not later than 15 days after the sponsor has first knowledge of the adverse reactions. For fatal or life threatening cases the term will be maximal 7 days for a preliminary report with another 8 days for completion of the report.

### 9.3 Annual safety report

In addition to the expedited reporting of SUSARs, the sponsor will submit, once a year throughout the clinical trial, a safety report to the accredited METC, competent authority, and competent authorities of the concerned Member States. This safety report consists of:

- a list of all suspected (unexpected or expected) serious adverse reactions, along with an aggregated summary table of all reported serious adverse reactions, ordered by organ system, per study;
- a report concerning the safety of the subjects, consisting of a complete safety analysis and an evaluation of the balance between the efficacy and the harmfulness of the medicine under investigation.

### 9.4 Follow-up of adverse events

All AEs will be followed until they have abated, or until a stable situation has been reached. Depending on the event, follow up may require additional tests or medical procedures as indicated, and/or referral to the general physician or a medical specialist. SAEs need to be reported until end of study within the Netherlands, as defined in the protocol.

### 9.5 Data Safety Monitoring Board (DSMB) / Safety Committee

Because we consider this a negligible risk study, we will not form a Data Safety Monitoring Board.

## 10. Statistical analysis

---

The data will be analysed in accordance with a statistical analysis plan that will be made before database lock. Due to the nature of this study, no formal statistical testing will be performed.

We will describe the primary endpoint parameters (iTTR, variance growth rate, SDTinr) by treatment group. The secondary endpoint parameter treatment satisfaction will be calculated as the difference between the score at randomisation and that at the end of study visit. This difference will be described per treatment group. The parameter medication errors will be summarised per treatment group and error severity.

To determine the feasibility of a full-scale RCT, we will calculate the size of the required patient population, based on the following assumptions and parameters:

- Significance level 0.05
- Power 0.80
- Effect size equal to the one found in this trial
- Inclusion ratio equal to the one found in this trial (i.e. percentage of selected patients that enrolls in the trials)

We will not perform interim analyses.

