## Study population

Patients aged 80 and above, who have been managed by Certe Trombosedienst for over 9 months, and use a daily dose of acenocoumarol between 0.5 and 2.0 milligram for any indication.

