### 4.3 Exclusion criteria

A potential subject who meets any of the following criteria will be excluded from participation in this study:

- Initiated therapy with acenocoumarol in the last nine months
- Expected termination of VKA within six months
- Dosing step lower than or equal to "step 7", i.e. usage of less than 3.5 milligrams acenocoumarol per week. Patients who use such a low dose generally have an unfavourable prognosis.
- Patients who determine the acenocoumarol dose themselves

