## 4.4 Sample size calculation

We performed a power analysis for a larger follow-up study, based on the following parameters:

Parameter	Value	Standard deviation
TTR control group	69 %	19
TTR intervention group	72.5%	17
Alpha (type I error rate)	5 %	
Failure rate	10 %	
Power (1 - type II error rate)	80 %	

The TTR values above are based on observational findings in our clinical practice. It should however be noted that the INR target ranges have been modified (c.q. narrowed) as per January 1st, 2016, and that we expect this will affect the TTR in both groups. This underlines the necessity of a pilot study.

This resulted in a needed sample size of 917 patients, which is much less than the 140 000 patients aged 80 and above managed by the Dutch Thrombosis Services.

For this pilot study we want to randomise 2 x 40 patients. This should give us an overview of the point estimates in the power analysis (which are currently based on observational data), and -more importantly- about the time investment needed to conduct a larger-scale study. Due to the inter-individual variation in response to VKA, we think a smaller sample could distort the view.

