### 8.2 Randomisation, blinding and treatment allocation

The study personnel will perform randomisation on-the-spot. To avoid technical difficulties, we will perform randomisation using ordered envelopes. We will stratify by INR target range (2.0-3.0 versus 2.5-3.5) within pre-specified blocks. The University Medical Center Groningen Pharmacy will provide randomisation lists.

Patients and professionals at the thrombosis service will know to which treatment group the patient has been randomised.

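### Section 10 names no adjustment for the randomisation stratum or earlier INR control and fixes PACT-Q2 as a raw change score, so the pilot gives up precision it could have at little cost

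*Protocol*

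**What the plan says.** The primary objective (Protocol Section 2) is to obtain an effect size for a full-scale RCT and to judge its feasibility. For the main parameters, Section 10 states: "We will describe the primary endpoint parameters (iTTR, variance growth rate, SDTinr) by treatment group". PACT-Q2 is to be scored as the difference between the randomisation and end-of-study values and described per group. The full-scale RCT is then sized on the effect observed in the pilot. No formal testing is planned, and a SAP is to be written before database lock.

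Two sources of precision appear elsewhere in the protocol but not in Section 10:

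- **Stratum.** Section 8.2: "We will stratify by INR target range (2.0-3.0 versus 2.5-3.5) within pre-specified blocks".
- **Earlier INR control.** Section 4.3 excludes anyone who meets "Initiated therapy with acenocoumarol in the last nine months". The Summary goes further and describes patients "who have been managed by Certe Trombosedienst for over 9 months". Section 8.1.2 says the service routinely collects the dates of INR measurements. However, the schedule in Section 8.3 starts follow-up data after the study visit and does not list the earlier INR series as study data.

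Section 3 has the first PACT-Q2 completed directly after randomisation, in an open-label trial.

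**The concern.** The effect estimate and its spread are what this pilot hands on. If both come from per-arm summaries alone, between-patient differences in INR control that existed before randomisation stay in the error term. Section 4.4 itself says that variation between patients in response to VKA could distort a small sample. Adjusting for each patient's earlier control addresses that variation directly.

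At stake are the width of the interval around the pilot effect, the SD used for sizing, and the correlation between earlier and on-study iTTR. The full-scale RCT would need that correlation if it is to adjust, and nothing in the protocol plans to estimate it. For PACT-Q2 the change score is a stated choice, and it is less efficient than baseline adjustment under ordinary conditions.

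**Working it through.** **Inputs.** Section 4.4 gives "TTR control group 69 % 19" and "TTR intervention group 72.5% 17" (mean, SD), alpha 5%, power 80%, failure rate 10%, and 40 patients per arm. The pre/on-study correlation r is not given; I assume 0.3 to 0.6.

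**1. The plan's own figure.** SD = √((19² + 17²)/2) = √325 = 18.03. With two-sided alpha, n per arm = 2 × 325 × (1.960 + 0.842)² / 3.5² = 416.5. The total is 833, or 834 when each arm is rounded up to 417. Then 833 × 1.10 = 916.3, rounded up to 917. The stated 917 reproduces.

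**2. Raw pilot precision for iTTR.** SE = √(19²/40 + 17²/40) = √16.25 = 4.03. The half-width is 1.96 × 4.03 = 7.9 points.

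**3. Adjusted for prior iTTR.** Regression adjustment multiplies the variance by 1 − r². The last column applies only if the full-scale RCT adjusts as well.

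| r (assumed) | Variance factor | SE | 95% half-width | Evaluable N, full RCT |
|---|---|---|---|---|
| none | 1.00 | 4.03 | 7.9 | 834 |
| 0.3 | 0.91 | 3.85 | 7.5 | 758 |
| 0.4 | 0.84 | 3.69 | 7.2 | 700 |
| 0.5 | 0.75 | 3.49 | 6.8 | 626 |
| 0.6 | 0.64 | 3.22 | 6.3 | 534 |

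The price in degrees of freedom is slight: at r = 0.5 the SE becomes about 3.51 instead of 3.49.

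**4. Stratum alone.** If INR range explains 2% to 10% of the variance (assumed), the SE is 4.03 × √0.98 = 3.99 to 4.03 × √0.90 = 3.82. Most of any gain would come from prior iTTR.

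**5. PACT-Q2.** Let r now be the correlation between the two scores, with equal variances σ². The change score has variance 2σ²(1 − r) and the baseline-adjusted score σ²(1 − r²). Their ratio is (1 + r)/2, below 1 for every r below 1.

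| r (assumed) | Change score (units of σ²) | Baseline-adjusted | Ratio |
|---|---|---|---|
| 0.3 | 1.40 | 0.91 | 0.65 |
| 0.5 | 1.00 | 0.75 | 0.75 |
| 0.6 | 0.80 | 0.64 | 0.80 |

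Below r = 0.5 the change score is noisier than the month-6 score with baseline ignored (variance 1.00).

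**6. Availability of the covariate.** The Summary requires more than nine months of management by this service. Sections 4.2 and 4.3 require current management there and no start of acenocoumarol in the last nine months. A patient who recently transferred in could satisfy the second pair without satisfying the first.

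**The case against.** The strongest reply is that covariate adjustment belongs to the SAP, which Section 10 announces and which is not shown. For the INR parameters this largely stands. Section 10 does not say that the effect carried forward must be unadjusted, so a reader who infers that adjustment is ruled out goes beyond the text. The reply does not cover PACT-Q2, where the change score is written into the protocol. Nor does it cover the data: an SAP can adjust only for records the study has extracted. The earlier INR series is not listed as study data, and Section 12.1 limits access to source data to the service's own professionals.

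It is also fair to say that the raw difference is unbiased under randomisation, that the gain rests on an assumed r, and that at r = 0.3 it is small. A usual-care correlation could also be taken from the service's own records, so the pilot is not its only possible source.

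Two stronger readings are tempting:

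- **Chance imbalance.** A reader might set the SE of a chance imbalance in prior iTTR (about 4 points, borrowing the outcome SDs) against the 3.5-point effect and conclude that imbalance can swamp it. With equal SDs only about r times the imbalance reaches the outcome: 0.3 × 4.03 = 1.2 to 0.6 × 4.03 = 2.4 points.
- **Complete records.** A reader might take it that every eligible patient already has nine months of INRs on file. Sections 4.2 and 4.3 guarantee nine months of therapy, not nine months of records at this service.

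**Conclusion.** The point holds as lost efficiency. It is not a bias or an error, and for the INR parameters Section 10 does not contradict itself. For iTTR, adjustment would cut the variance by 9% to 36% and bring the half-width from 7.9 to between 7.5 and 6.3 points. This assumes r of 0.3 to 0.6, a linear relation and all 40 patients per arm analysed. For PACT-Q2 the variance saving is 35% to 20% over the same range of r, 25% at r = 0.5, given equal variances at the two times.

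A reader might infer that adjustment would make the pilot effect a sound basis for sizing. The figures do not support that: even at r = 0.6 the half-width (6.3) exceeds 3.5 points, and the chance of a wrong-signed estimate when the true effect is 3.5 falls only from 19% to 14%. The drop in the full-scale N from 834 to between 758 and 534 follows only if that trial also adjusts.

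**What to change.** In Section 10:

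- For iTTR, variance growth rate and SDTinr, report the between-group difference with 95% CI from a linear model with treatment, INR-range stratum and the same parameter over the 6 months before randomisation. Score the earlier period on the patient's current target range, since Section 4.4 notes that ranges were narrowed in January 2016. Keep the raw per-arm summaries beside it.
- Report the residual SD and the pre/on-study correlation, and use them for sizing if the full-scale RCT will also adjust.
- Analyse month-6 PACT-Q2 adjusted for the baseline score in place of the raw change. State that under Section 3 this baseline is completed directly after open-label randomisation, so knowledge of allocation may have affected it.

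Elsewhere, add the prior-INR extract to the planned study data, and reconcile the Summary with Sections 4.2 and 4.3 on whether nine months of management by this service is required.

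The cost is one extra extract from routine records, a little more analysis and a few degrees of freedom. No visit or measurement is added.

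### Section 10 sizes the full-scale RCT on the difference observed in 2 x 40 patients, whose standard error exceeds the planned difference, so the recalculated sample size is unreliable

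*Protocol*

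**What the plan says.** Section 2 makes effect-size data and the feasibility of a full-scale RCT the primary objective. Section 10 plans no formal testing. It assesses feasibility by calculating the required patient population at a significance level of 0.05 and power of 0.80, with "Effect size equal to the one found in this trial" and with the inclusion ratio seen in the pilot. It sets no target difference, no interval or range around the observed effect, and no rule for a zero or negative estimate.

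Section 4.4 already holds a power analysis for the larger study, with TTR as the outcome, and reports: "This resulted in a needed sample size of 917 patients". Of the pilot's 2 x 40 patients it says: "This should give us an overview of the point estimates in the power analysis". It ranks knowledge of the time investment above this. It describes its TTR values as observational, and expects the INR target ranges, narrowed from January 2016, to change TTR in both groups.

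**The concern.** The required N varies with the inverse square of the difference entered, so error in the difference is magnified in N. Section 10 enters a single estimate from 80 patients as if it had no error. A pilot that overshoots by chance gives an N that is too small to detect the true effect. One that undershoots gives an N so large that the RCT looks infeasible. One with the wrong sign gives no meaningful N, although the formula still returns a number because the difference is squared. Any of these can happen when the hypothesis is true, and a small, attractive N can also appear when it is false. This is the sample-size part of the feasibility assessment, and it is the only feasibility calculation that Section 10 describes. The protocol fixes the rule itself, so an SAP that follows the protocol would carry it forward.

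**Working it through.** **Inputs (Section 4.4).** "TTR control group 69 % 19" and "TTR intervention group 72.5% 17", i.e. means 69 and 72.5 with SDs 19 and 17, so a planned difference of 3.5 points. "Alpha (type I error rate) 5"%, "Power (1 - type II error rate) 80"%, "Failure rate 10"%. Pilot: 40 per group.

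**1. The plan's own figure.** For two equal groups, total N = 2 x (1.96 + 0.8416)² x (SD₁² + SD₂²) / d². With SD₁² + SD₂² = 361 + 289 = 650 and d = 3.5:

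N = 2 x 7.849 x 650 / 12.25 = 833, or 417 per group and 834 in total. Adding 10% gives 834 x 1.10 = 917, the stated figure. Dividing by 0.9 gives 927. A one-sided alpha gives 724 to 732 and does not reproduce it. The 917 is not in dispute, and it confirms the inputs. All N below are evaluable patients, before the failure allowance.

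**2. Precision of the pilot difference.**
- 40 per group: SE = √(650/40) = 4.03; 95% half-width 1.96 x 4.03 = 7.9. An observed 3.5 would have a CI of -4.4 to +11.4.
- 36 per group (10% failure): SE = √(650/36) = 4.25; half-width 8.3.

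**3. Chance of a zero or negative estimate when the truth is 3.5.** Φ(-3.5/4.03) = Φ(-0.868) = 0.19 (0.21 with 36 per group).

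**4. Distribution of the recalculated N when the truth is 3.5.** I simulated 400,000 pilots of 40 per group, sampling the difference and both SDs, and applied the formula in step 1. Among pilots with a positive difference, the quartiles of N are about 210, 500 and 1,730. Counting all pilots, only 24% give a positive estimate and an N within a factor of two of 834.

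**5. True power of an RCT of that size.** With the SDs held at plan, power = Φ(2.8016 x 3.5/d_obs - 1.96).
- It falls below 80% when d_obs exceeds 3.5, which has probability 0.50 over all pilots and 0.50/0.81 = 0.62 among positive ones.
- It falls below 50% when d_obs exceeds 3.5 x 2.8016/1.96 = 5.0. The probability is 1 - Φ((5.0 - 3.5)/4.03) = 0.35. With the SDs also sampled it is 0.36 over all pilots and 0.44 among positive ones.

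| True difference 3.5, 40 per group | Positive pilots | All pilots |
|---|---|---|
| Positive pilot giving RCT power below 80% | 62% | 50% |
| Positive pilot giving RCT power below 50% | 44% | 36% |

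**6. If the true difference is zero.** An N of at most 834 needs d_obs of about 3.5 or more: 1 - Φ(3.5/4.03) = 0.19.

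**7. The alternative.** With d fixed at 3.5 and only the SDs taken from the pilot, N lies between about 590 and 1,120 in 95% of simulated pilots (591 to 1,116).

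**8. Sensitivity to the SD.** The SE drops below 3.5 only if the common SD is below 3.5 x √20 = 15.7. Even then the 95% half-width is 1.96 x 3.5 = 6.9, about twice the planned difference.

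**The case against.** The strongest defence is that this is a pilot without formal testing and that it serves more than one purpose. Section 4.4 puts time investment first, and Section 10 also uses the inclusion ratio. Neither depends on the between-group difference. This stands. A reader might infer that the pilot's main output is close to arbitrary, but the documents support that only for the recalculated N.

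Nothing in the protocol binds the sponsor to run the next trial at that N. The 917 in Section 4.4 can be set beside it, and the later RCT would need its own protocol. This also stands: the power figures describe what follows if the calculated N is adopted. No participant or analysis of the pilot itself is harmed. But a calculation made to inform the decision should not depend so heavily on chance.

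The narrowed INR ranges are a sound reason to re-estimate the planning values. They justify updating the SDs and the control mean, which 40 per group can usefully inform. They do not make the difference estimable.

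Three stronger readings are not supported. One is that the plan leaves open which of the three main parameters supplies the effect size: Section 4.4 sizes on TTR, and such detail may sit in an SAP that is not at hand. Another is that Section 4.4 promises to verify its point estimates: it promises only an overview. The third is that 3.5 points is the smallest difference worth detecting: the protocol gives it as an observational value.

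**Conclusion.** The point holds for the effect-size bullet in Section 10. On the protocol's own planning values, one standard error of the pilot difference (4.0) already exceeds the difference to be detected (3.5). The N computed from it is thus as likely as not to underpower the RCT, and it separates a true 3.5-point effect from no effect poorly. The figures assume that TTR is the sizing parameter, that the SDs are 19 and 17, that the estimated difference is approximately normal, that the analysis is unadjusted and that alpha is two-sided. The SDs may change under the narrowed target ranges, but step 8 shows that a plausible fall would not rescue the rule. The inclusion ratio, the time-investment data and the 917 are untouched.

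**What to change.** In Section 10, replace the effect-size bullet with a target TTR difference fixed before any outcome data are seen. The 3.5 points in Section 4.4 can serve as a planning value. However, the sponsor should justify it as worth detecting, because it is observational and the protocol itself expects the narrowed ranges to shift TTR. Take the SDs, inclusion ratio and failure rate from the pilot, and show N over a range of SDs. Report the observed difference with its 95% CI, but do not use it as the sizing input.

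In Section 4.4, keep the sentence on point estimates and add that 2 x 40 patients cannot estimate the between-group difference precisely enough to size the RCT. Check that the reference to effect size in the Summary and Section 2 still reads correctly beside this.

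The cost is a few lines of text, carried into the SAP, with no extra patients or procedures. The real demand is that the sponsor must commit to a target difference in advance and defend it.
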